# Relationship Between Acute Phase Markers and Post-operative Pain in Laparoscopic Cholecystectomy: An Observational Study

March 3, 2023

**Background:** Many patients undergoing laparoscopic cholecystectomy are prone to developing acute and chronic post-operative pain.

The aim of the study is to show a possible correlation between pain and acute phase proteins in order to:

- predict the severity of pain;
- select most suitable pain relief therapy for the patient.

**Materials and methods:** The day after surgery, some serum markers are determined by a blood sample. The markers analyzed are:

- Leukocytes;
- C-reactive protein (CRP);
- D-dimer;
- Fibrinogen;
- Neutrophil-to-Lymphocyte Ratio (NLR).

Pain level is assessed using the NRS scale at different times:

- 1st post-operative day;
- 7th post-operative day;
- One month after surgery;
- Three months after surgery;
- Six months after surgery.

Other data collected for the study are: gender, age and BMI.

**SAP:** Statistical Analysis Plan was expressed as percentages, median, and range of values. Differences between continuous variables were analyzed with the Mann-Whitney U test, whereas differences between categorical variables were evaluated with the chi-square or the Fisher's exact test, when appropriate. Variables achieving statistical significance ( $P<0.05$ ) at univariate analysis were entered in a backward multivariate logistic regression model, removing the variable if  $P$  more than 0.10.  $P$  less than 0.05 was considered statistically significant. Statistical analysis was carried out with the SPSS software packaging (SPSS Inc., Chicago, IL), version 13.

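### Conversion to open surgery and complications present by the day-1 sample are not collected, so the analysis cannot show whether a marker says anything about pain beyond a complicated operation

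*Combined protocol and SAP*

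**What the plan says.** The document is a single short text, and its Materials and methods paragraph lists everything to be collected.

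- **Markers.** "The day after surgery, some serum markers are determined by a blood sample": leukocytes, CRP, D-dimer, fibrinogen and NLR. No second sample is described.
- **Outcome.** "Pain level is assessed using the NRS scale at different times": day 1, day 7, and one, three and six months.
- **Everything else.** "Other data collected for the study are: gender, age and BMI".

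The Background paragraph gives the purpose: "The aim of the study is to show a possible correlation between pain and acute phase proteins in order to" predict how severe pain will be and choose the pain relief therapy that suits the patient.

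The SAP paragraph takes variables that are significant in univariate analysis. These "at univariate analysis were entered in a backward multivariate logistic regression model, removing the variable if" P exceeds 0.10. Significance is set by P "less than 0.05 was considered statistically significant".

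Conversion to open surgery, complications, re-intervention and readmission are mentioned nowhere. There are no eligibility criteria, no sample size, and no expected rate for any of these events.

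**The concern.** All five markers are non-specific: they respond to tissue injury, inflammation or activation of coagulation. A converted operation causes a larger wound before the sample is drawn. Bleeding, a bile leak or an infection already under way on day 1 could raise the markers, and each could also raise pain. Such events would be common causes of the two quantities being correlated. That they act this way is a clinical assumption, reasonable but not stated in the document.

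Under the plan, a converted or early-complicated patient enters the analysis exactly like an uneventful one. A variable that is not collected cannot be a candidate in the regression, a stratum or a reason for exclusion in a sensitivity analysis.

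What is at stake is the interpretation of a positive result. If the association comes from a small group of complicated operations, the marker reports something the surgical team may already know. Using it to choose analgesia would then rest on the wrong explanation. The prediction aim is less exposed, because a marker that predicts pain by way of surgical trauma still predicts pain.

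**Working it through.** **1. What can be a common cause.** The markers are measured once, the day after surgery, while pain is followed for six months. Setting that timing against each kind of event gives:

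| Event | Can raise the day-1 marker | Can raise pain |
|---|---|---|
| Conversion to open surgery | Yes, it precedes the sample | Yes |
| Complication under way by the sample | Yes | Yes |
| Complication, re-intervention or readmission starting after the sample | No | Yes, at later times only |

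Only the first two rows can produce a spurious marker-pain correlation.

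**2. Whether the analysis can deal with it.** Candidates for the model come from the collected variables: five markers, gender, age and BMI. None of these records conversion or a complication, so the regression cannot adjust for either.

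**3. How large the effect could be.** The plan gives no figure to reproduce. The inputs below are assumptions:

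- p, the proportion converted or with a complication by the sample: 2%, 5%, 10%.
- d1, the marker shift in these patients, in within-group SDs: 1, 2 or 2.5.
- d2, the NRS shift, in within-group SDs: 1 or 1.5.
- No marker-pain association within either group; normal distributions within groups.

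Pearson correlation, with v = p(1−p):

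r = v·d1·d2 / √[(1 + v·d1²)(1 + v·d2²)]

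Example, p = 0.10, d1 = 2.5, d2 = 1.5: v = 0.09; numerator 0.09 × 2.5 × 1.5 = 0.3375; denominator √(1.5625 × 1.2025) = 1.371; r = 0.246.

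The planned univariate test for continuous variables is the Mann-Whitney U, which uses ranks, so the rank (Spearman) version is also relevant:

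r_s = 12·v·(A1 − 0.5)(A2 − 0.5), with A = Φ(d/√2)

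Same example: A1 = Φ(1.768) = 0.9615; A2 = Φ(1.061) = 0.8556; r_s = 12 × 0.09 × 0.4615 × 0.3556 = 0.177.

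| p | (d1, d2) | Pearson | Rank-based |
|---|---|---|---|
| 2% | (1, 1) | 0.019 | 0.016 |
| 2% | (2, 1) | 0.037 | 0.026 |
| 2% | (2.5, 1.5) | 0.068 | 0.039 |
| 5% | (1, 1) | 0.045 | 0.039 |
| 5% | (2, 1) | 0.085 | 0.063 |
| 5% | (2.5, 1.5) | 0.149 | 0.094 |
| 10% | (1, 1) | 0.083 | 0.073 |
| 10% | (2, 1) | 0.148 | 0.118 |
| 10% | (2.5, 1.5) | 0.246 | 0.177 |

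**4. Whether it would be declared significant.** The N giving 80% power at two-sided 0.05 is ((1.960 + 0.842)/atanh r)² + 3. The plan does not say whether its test is two-sided; that is assumed. At p = 10%, the Pearson values need about 1150 patients for (1, 1), 357 for (2, 1) and 128 for (2.5, 1.5). The plan states no sample size, so it is unknown which of these applies.

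**The case against.** The case against has four parts.

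*Timing.* A reader might infer that every complication, re-intervention or readmission in six months confounds the result. The document does not support this. With one sample the day after surgery, an event that begins later cannot have raised the marker. This objection stands, and it limits the point to conversion and complications already under way by the sample.

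*Prediction does not need a causal marker.* The document speaks of a possible correlation used to predict severity, and does not claim that the marker measures a patient's own tendency to pain. A confounded marker can still predict. This also stands for the first aim. It does not remove the problem for the second, choosing pain relief therapy, where it matters whether the marker adds anything to what the operation already shows.

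*Size.* A reader might infer that the study would detect only complicated operations. That is the extreme case. The rates and shifts have no source in the document, and with 1 SD shifts the spurious correlation stays below 0.09 even at 10%. For (2, 1) and (2.5, 1.5), the rank-based values are 20% to 43% below the Pearson ones. This stands as a limit on the size. Without the data, though, the study cannot show where in the range it lies.

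*Converted cases might not be in the cohort.* The title refers to laparoscopic cholecystectomy, but nothing says whether converted patients stay in. The conversion part of the point is therefore conditional on their being included.

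**Conclusion.** The point holds in a limited form. Conversion and complications present by the day-1 sample are plausible common causes of marker and pain. They are not collected, and the planned regression cannot adjust for them. The study therefore cannot say whether a marker carries information about pain beyond an evidently complicated operation. Of the two aims, this mainly weakens the choice of pain relief therapy.

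The size is unknown: from negligible to modest across the assumed range, about 0.02 to 0.25 as a Pearson correlation or 0.02 to 0.18 on ranks. This rests on assumed event rates and shifts, on no association within groups, and on the clinical premise that these events raise both quantities.

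It should be corrected because the correction is cheap, and because without it the bias can be neither measured nor ruled out.

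**What to change.** Add to the collected data, from the operative note and routine chart: conversion to open surgery (yes/no), and any complication, re-intervention or readmission with its date. State whether converted patients stay in the cohort.

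Report the marker-pain results twice:

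1. For all patients.
2. Adjusted for conversion or a complication present by the time of the day-1 sample, or restricted to patients with neither. If adjustment is used, keep this term in the model whatever its P value; a rare factor could otherwise fail the univariate screen or be dropped in the backward step.

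Describe a marker as informative beyond surgical complexity only if the association persists in the second analysis.

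Excluding patients with later complications is acceptable as a descriptive sensitivity analysis for the later NRS times. It should not be the condition for the claim. It selects patients on events after the marker was measured, which are unknown when a prediction would be used and may lie on the path from early inflammation to later pain.

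The cost is a few chart fields and one additional analysis, with no new procedure or visit. The downside is slightly fewer patients in the restricted analysis.

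### The aim is a correlation between acute phase markers and pain severity, but the SAP names no correlation measure and relies on grouping that it does not define

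*Combined protocol and SAP*

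**What the plan says.** The Background states: "The aim of the study is to show a possible correlation between pain and acute phase proteins in order to", followed by two purposes: "predict the severity of pain" and "select most suitable pain relief therapy for the patient".

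Materials and methods describes the data. On the markers: "The day after surgery, some serum markers are determined by a blood sample". Five are listed: leukocytes, CRP, D-dimer, fibrinogen and NLR. No cut-off is given for any of them. On the outcome: "Pain level is assessed using the NRS scale at different times", namely day 1, day 7, and one, three and six months. The covariates are also listed: "Other data collected for the study are: gender, age and BMI".

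The SAP paragraph is the only statistical text. It gives percentages, median and range as summaries. For testing it says "Differences between continuous variables were analyzed with the Mann-Whitney U test", and it assigns chi-square or Fisher's exact test to categorical variables. Variables with P<0.05 go into a backward logistic model, with removal at P above 0.10. No correlation coefficient is named, and no linear, ordinal or repeated-measures model. The paragraph does not say which groups are compared, what the logistic outcome is, where the NRS would be cut, or which of the five time points the analysis uses.

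**The concern.** The aim asks how a marker level goes with the degree of pain. The listed methods ask whether groups differ, or what the odds of a category are. If the plan is followed, the report will contain P values for group differences and odds ratios for a pain category that is still to be chosen. It will contain no estimate of the strength of the relation that the aim names.

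The grouping is not a minor detail here. With five markers, five visits and no fixed NRS cut, the analyst has to choose a split and a visit before any listed test of a marker against pain can be run. Nothing in the SAP prevents that choice from being made after the results are known, and P values obtained that way could not be taken at face value.

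**Working it through.** **Step 1. Aim against methods.** The plan states no sample size, power or target correlation, so there is no figure to reproduce. The check is to go through each listed method.

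- *Percentages, median, range:* describe one variable at a time.
- *Mann-Whitney:* needs a two-level grouping. Either pain is cut and the marker is compared, or the marker is cut and the NRS is compared.
- *Chi-square or Fisher:* both pain and marker must be categories. The order of any pain bands is ignored.
- *Logistic regression, as ordinarily meant:* the marker may stay continuous, but pain becomes a binary outcome.

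None of these, read naturally, relates a continuous marker to the ungrouped NRS. This step needs no assumption about numbers.

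**Step 2. Does grouping cost power?** Every input here is assumed, because the documents give none: n=100, two-sided 0.05, an NRS of 0-10, and two score distributions.

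- Early-visit-like shares for scores 0 to 10: .05 .10 .15 .20 .15 .12 .09 .07 .04 .02 .01
- Late-visit-like shares: .60 .12 .09 .07 .05 .03 .02 .01 .005 .003 .002

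*Scenario A, smooth monotone relation.* Marker and latent pain are bivariate normal with correlation 0.30, and latent pain is mapped to the scores (8000 replicates). Spearman's power on the full NRS is 82.4% early and 71.0% late. Mann-Whitney on the marker, with pain split at the score shown or above:

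| Pain cut | Early: power | Early: difference | Late: power | Late: difference |
|---|---|---|---|---|
| 1 | 26.1% | 82.4 - 26.1 = 56.3 | 64.5% | 71.0 - 64.5 = 6.5 |
| 4 | 65.7% | 16.7 | 43.2% | 27.8 |
| 5 | 62.6% | 19.8 | 32.6% | 38.4 |
| 7 | 47.1% | 35.3 | 11.8% | 59.2 |

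The two largest differences come from extreme cuts. Early, a cut at 1 leaves 5% of patients in the smaller group. Late, a cut at 7 leaves .01+.005+.003+.002 = 2%. Without those two cells the range is about 7 to 38 points. Splitting the marker at its median and leaving the NRS uncut gives 65.2% early and 53.8% late.

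At zero correlation Spearman rejects in 4.6% (early) and 4.8% (late) of runs and the grouped tests in 2.4% to 5.1%, so the higher power is not bought with excess false positives.

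*Scenario B, threshold relation.* The marker is shifted only in patients at or above the pain cut of 4, and Mann-Whitney uses that same cut. Early, with a shift of 0.6 SD: Mann-Whitney about 83%, Spearman about 71%. Late, with a shift of 0.8 SD: about 67% against 33%. The order reverses. A cut placed exactly at the true threshold is the best case for Mann-Whitney.

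**Step 3. What the missing estimate would look like.** In Scenario A the mean rho is 0.283 (SD 0.094) early and 0.250 (SD 0.095) late. At n=100 the 95% CI half-width is about 1.96 x 0.094 = 0.18 to 1.96 x 0.095 = 0.19. The listed methods do not promise any such estimate with an interval.

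**The case against.** The strongest reply is that correlation here means association. The aim speaks of a possible correlation and the title of a relationship. Mann-Whitney and logistic regression can show an association between a marker and high against low pain, and a Mann-Whitney statistic converts to a rank-biserial correlation. This stands in part: the aim is not wholly unaddressed. But the plan does not promise that conversion, the two groups are undefined, and high against low is coarser than the severity that the aim names.

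A second reply is that logistic regression could be ordinal. It could in principle. The text does not say so, and entry to the model would still depend on univariate tests that need groups.

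A third is that a binary model also predicts severity. It does, coarsely, and a binary split may suit the second purpose, choosing pain relief. It would be too strong to say that a binary outcome cannot serve prediction at all.

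A fourth is that the power comparison favours rank correlation because it assumes a smooth relation. That stands, as Scenario B shows. A reader might infer that grouping always loses power; the documents give no sample size, effect size or score distribution from which to say so.

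Finally, one could keep a binary outcome, fix the cut and visit in advance, and restate the aim as association with that category. That would remove the contradiction, but at the price of a narrower aim.

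**Conclusion.** The concern holds in this form: the SAP names no correlation measure, its listed methods as ordinarily meant need pain or the marker to be grouped, and the groups, NRS cut, logistic outcome and time point are not given. The plan can therefore show association with a pain category but does not estimate how strongly a continuous marker relates to graded pain. That conclusion rests on the text alone and bears on the study's only stated aim.

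The power figures are illustrative and carry none of the weight. Under the assumed smooth relation Spearman had more power at every simulated pain cut, by about 7 points to over 50. Under the assumed shift only above the cut, Mann-Whitney had more.

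A reader might also infer that the grouping was, or will be, chosen from the results. The documents do not show this. The SAP is in the past tense and a document dated March 2023 cites a paper from August 2023, but neither fact establishes whether outcome data had been examined. What can be said is that the plan leaves the choice open.

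**What to change.** 1. Name one primary NRS time point in advance. Day 7 is the first score certain to follow the blood sample, because the plan does not give the order of the day-1 sample and the day-1 score. A later visit is equally defensible if chronic pain is the main interest; the Background describes patients as "prone to developing acute and chronic post-operative pain".
2. At that time point, make the main analysis Spearman's rho with a 95% CI between each of the five continuous markers and the full NRS.
3. Support it with a proportional-odds model of the full NRS, one per marker, adjusted for age, gender and BMI, and check the proportional-odds assumption. Spearman's rho does not depend on it.
4. Treat the other four time points as secondary. Keep the group tests and the logistic model as secondary, with one pain cut fixed in advance.
5. If outcome data have already been examined, label the revised analysis post hoc.

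The cost is small: the same patients, visits and data, a change of SAP wording, slightly more analysis, one assumption to check, and less emphasis on four of the five visits. If the data have been seen, the new analysis also loses confirmatory weight.

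Adjustment across the five markers, replacement of backward selection and optimism-corrected concordance are separate, optional points. This defect does not require them.

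### Variables are selected and their odds ratios estimated in the same patients without correction, so selected markers will tend to look too strong and their final P values are not independent confirmation

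*Combined protocol and SAP*

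**What the plan says.** The SAP is one unnumbered paragraph in the combined document. Its modelling rule has three steps, all applied to the same patients:

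1. **Screen.** "Differences between continuous variables were analyzed with the Mann-Whitney U test", and "differences between categorical variables were evaluated with the chi-square or the Fisher's exact test", whichever suits. "Variables achieving statistical significance ( $P<0.05$ ) at univariate analysis" go forward.
2. **Backward removal.** These variables "were entered in a backward multivariate logistic regression model, removing the variable if" its P value is "more than 0.10".
3. **Claim.** A P value "less than 0.05 was considered statistically significant".

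The candidates are five serum markers (leukocytes, CRP, D-dimer, fibrinogen, NLR), plus gender, age and BMI if these are screened too. One stated purpose is to "predict the severity of pain".

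The text mentions no bootstrap, cross-validation, shrinkage, validation sample or prespecified model. It gives no sample size, number of events or expected effect, and no NRS cut-off to define the binary outcome that logistic regression needs.

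**The concern.** A variable reaches the final model only if its association in these patients was strong enough to pass the screen and survive removal. Its odds ratio, standard error and P value are then read as if the model had been fixed in advance. Among variables that pass, overestimates are over-represented, so the average reported odds ratio lies further from 1 than the truth. The final test uses the same patients as the screen, so a second P<0.05 is largely expected once the first has occurred.

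This differs from the question of how many tests are done. A stricter threshold lowers the number of false positives but increases the exaggeration of a true marker that passes it.

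Prediction is what is at stake. Coefficients that are too large give predicted risks that are too extreme in the next patients. A marker described as an independent predictor may also be read as having been tested twice.

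**Working it through.** The plan gives no figure to reproduce. The thresholds (0.05, 0.10, 0.05), the tests and the list of candidates come from the document. The following are assumptions: 8 candidates, 30% of patients with the pain outcome, one true marker, two-sided tests, n of 100, 200 and 400, and true odds ratios (OR) per SD of 1.3, 1.5 and 2.0.

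**Step 1: the smallest odds ratio that can be significant.** For a standardised marker, SE(log OR) ≈ 1/√(n × 0.3 × 0.7), and P<0.05 needs |log OR| > 1.96 × SE.

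- n=100: SE = 1/√21 = 0.218; 1.96 × 0.218 = 0.428; OR above exp(0.428) = 1.53.
- n=200: SE = 1/√42 = 0.154; 1.96 × 0.154 = 0.302; OR above 1.35.
- n=400: SE = 1/√84 = 0.109; 1.96 × 0.109 = 0.214; OR above 1.24.

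At n=100, a marker with a true OR of 1.3 or 1.5 can be significant only if it is overestimated. At n=400 neither has to be.

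**Step 2: average among significant results, by formula.** With β = log OR and c = 1.96 − β/SE, the mean of a normal estimate given that it passes is β + SE × φ(c)/[1 − Φ(c)]. This neglects passing in the wrong direction.

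- True OR 1.3, n=100: β = 0.262, c = 0.758; 0.262 + 0.218 × 0.299/0.224 = 0.554, so OR 1.74.
- True OR 1.3, n=200: c = 0.260; 0.262 + 0.154 × 0.386/0.398 = 0.412, so OR 1.51.
- True OR 2.0, n=200: β = 0.693, c = −2.53; 0.693 + 0.154 × 0.016/0.994 = 0.696, so OR 2.0.

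**Step 3: simulation of the written rule.** Mann-Whitney or chi-square screen at 0.05, backward removal at 0.10, final P<0.05, independent candidates. The entries are the geometric mean OR of the true marker when it is reported as significant. In brackets is its log divided by the true log OR; for example, ln 1.86/ln 1.3 = 0.621/0.262 = 2.4.

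| True OR | n=100 | n=200 | n=400 |
|---|---|---|---|
| 1.3 | 1.86 (2.4) | 1.56 (1.7) | 1.40 (1.3) |
| 1.5 | 1.96 (1.7) | 1.65 (1.2) | 1.53 (1.05) |
| 2.0 | 2.23 (1.16) | 2.04 (1.03) | 2.01 (1.01) |

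These follow the pattern of step 2 and lie slightly higher, because logistic estimates are also somewhat too large in small samples. Correlation of 0.5 among markers gives similar inflation.

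**Step 4: is selection the cause?** An unselected model with all 8 candidates gives 1.34 at n=100 and 1.33 at n=200 for a true OR of 1.3, and 1.59 and 1.54 for 1.5. Most of the excess in step 3 therefore comes from selection.

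**Step 5: the final P value.** With independent candidates and one true marker, a null variable that passes the screen ends at P<0.05 in about 65% to 76% of cases. If every candidate is null, the figure is 70% to 82% (62% to 67% with correlation 0.5). The nominal rate is 5%. When a null marker is correlated 0.5 with a true one, the figure falls to about 5% to 57%.

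**The case against.** A reader might infer that every surviving marker has an exaggerated odds ratio. The rule does not imply that. The bias is an average that depends on power. For a true OR of 2.0 at n=200 to 400, about half of the retained estimates lie above the truth (52% to 53%, or 48% with correlation 0.5). The plan gives neither sample size nor effect, so a study with almost no bias is possible. This part of the objection stands.

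A reader might also infer that the final P value is worthless. It is not: it asks whether a marker adds to the others. With correlation 0.5, a true OR of 2.0 and n=400, only 6% of null variables that entered ended at P<0.05. Leukocytes and NLR come from the same blood sample and both depend on neutrophils, so correlation is the more plausible case. This stands too: the P value is anti-conservative after selection but still informative.

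Third, the SAP does not promise odds ratios or a risk score, and the aim is worded as showing a possible correlation. That limits what can be said about a future report. However, prediction is a stated purpose, and a logistic model's coefficients are log odds ratios.

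Finally, bootstrap shrinkage is imperfect. In trial runs with 100 resamples, an average of 1.84 fell only to 1.50 (truth 1.3, n=100), while 2.05 became 1.86 (truth 2.0, n=200). One slope under-corrects weak markers in small samples and over-shrinks strong ones. The fix is worded with that limit.

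None of this removes the central point. Nothing in the plan secures the large sample or strong effects under which the bias becomes small.

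**Conclusion.** The concern holds as a statement about tendency. Selection and estimation in one cohort without correction will tend to exaggerate the odds ratios of selected markers, and the final P value is not independent confirmation. The exaggeration is marked for modest effects in small samples (log OR about 2.4 times too large for a true OR of 1.3 at n=100). It is moderate in between (about 1.2 times for 1.5 at n=200) and negligible for 2.0 from n=200. The documents do not support the stronger statements that any surviving marker must be exaggerated or that the final P value confirms nothing.

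The figures rest on the assumed 8 candidates, 30% event rate, sample sizes and effects. The real size cannot be fixed until the sponsor states the sample size and the pain cut-off.

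**What to change.** Add to the SAP:

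1. Repeat the whole procedure (screen, backward removal, final fit) in at least 500 bootstrap samples. Resampling only the final model would miss the selection.
2. Report how often each variable is retained and the optimism-corrected calibration slope.
3. Apply that slope to any predicted risks. Show shrunken beside unshrunken odds ratios, with a note that a single slope corrects calibration and not each marker's selection bias.
4. State that final-model P values are post-selection and that results are exploratory until validated in new patients.

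The sample size and the definition of the binary pain outcome must be stated first, because the bootstrap cannot be specified without the outcome.

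The cost is SAP wording and computing time, with no new data. Reported odds ratios will be less favourable, and strong markers will be shrunk somewhat too far. Prespecifying the model would avoid selection altogether, but in a very small sample an unselected 8-variable model is itself overfitted: at n=50 it returned 1.77 for a true OR of 1.5. Shrinkage would still be needed there.

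### Five unranked markers are judged at an unadjusted P<0.05 against an undefined binary pain outcome, with no primary time point, multiplicity rule or exploratory label

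*Combined protocol and SAP*

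**What the plan says.** The document has three short unnumbered parts: Background, Materials and methods, and SAP.

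- **Background.** "The aim of the study is to show a possible correlation between pain and acute phase proteins". Two purposes follow: predicting how severe pain will be, and guiding the choice of pain treatment. The analysis is not labelled exploratory or hypothesis-generating.
- **Materials and methods.** "The markers analyzed are" introduces five entries: leukocytes, CRP, D-dimer, fibrinogen and NLR. "Pain level is assessed using the NRS scale at different times" introduces five: day 1, day 7, and one, three and six months. Neither list is ranked. "Other data collected for the study are: gender, age and BMI".
- **SAP.** Continuous variables are compared by Mann-Whitney, and categorical ones by chi-square or Fisher. "Variables achieving statistical significance" at P<0.05 in the univariate step "were entered in a backward multivariate logistic regression model", with removal when P exceeds 0.10. Last, P "less than 0.05 was considered statistically significant".

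The SAP does not say which groups the univariate tests compare, how the NRS becomes binary, which times are analysed or how many models are fitted. It also does not say whether gender, age and BMI pass through the same screen. No sample size is given.

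**The concern.** Two gaps compound each other. A Mann-Whitney comparison of marker values and a logistic model both need patients split into two groups. Because the split is not defined, neither the pain outcome nor the number of tests is fixed. On top of that, the plan names no primary marker or time point, adjusts nothing, and does not say that the results are exploratory.

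A marker could therefore be reported as a predictor of pain severity because it passed 0.05 in one of an uncounted set of tests, and a reader could not tell which test had been intended. What is at stake is the strength of the study's main claim.

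**Working it through.** The plan states no overall error rate, power or sample size, so there is no derived figure to reproduce. Its only error rate is 0.05 per test.

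**Inputs from the document:** threshold 0.05 for screen and final result; removal above 0.10; 5 markers; 5 NRS times; 3 further variables.

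**Assumed, because the document is silent:** two-sided tests; n = 60, 100 or 200; 30% of patients in the higher-pain group (20% and 50% also tried at n = 100); correlations from 0 to 0.9.

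**Step 1: number of tests.** One pain outcome gives 5 × 1 = 5 marker tests. Every marker at every time gives 5 × 5 = 25. If gender, age and BMI are screened too, these become 8 and 40.

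**Step 2: ceiling for the screen alone.** With k independent tests and no true association, P(at least one P<0.05) = 1 − 0.95^k.

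- k = 5: 0.226
- k = 8: 0.337
- k = 25: 0.723
- k = 40: 0.872

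**Step 3: the full rule.** Step 2 ignores correlation and the backward step, so the whole rule was simulated with no marker related to pain. Five normal markers had common correlation rm. Five underlying pain scores had common correlation rt, and each score was cut at the assumed higher-pain share. The rule was a Mann-Whitney screen at 0.05, backward logistic regression with removal at P>0.10, and P<0.05 in the final model. Each cell used 4,000 data sets, so the Monte Carlo standard error is at most √(0.25/4000) = 0.008. Results for a 30% share, range over the three sample sizes:

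| rm, rt | One outcome: screen | One outcome: full rule | Five times: screen | Five times: full rule |
|---|---|---|---|---|
| 0, 0 | 0.218-0.235 | 0.166-0.184 | 0.710-0.715 | 0.593-0.622 |
| 0.5, 0.5 | 0.182-0.193 | 0.136-0.151 | 0.599-0.608 | 0.490-0.521 |
| 0.7, 0.7 | 0.149-0.156 | 0.115-0.117 | 0.480-0.491 | 0.381-0.411 |
| 0.9, 0.9 | 0.108-0.113 | 0.083-0.090 | 0.286-0.290 | 0.224-0.243 |

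With a 20% or 50% share (n = 100), the full rule gives 0.085-0.171 for one outcome and 0.220-0.613 for five times.

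These correlations apply to the underlying scores before they are cut in two, and cutting weakens them. If 0.7 is instead applied directly to the test statistics, the screen gives 0.147 for 5 tests and 0.388 for 25.

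**Step 4: cost of Holm over five markers.** The thresholds are 0.05/5 = 0.01, then 0.0125, 0.0167, 0.025 and 0.05. A comparison with 80% power at two-sided 0.05 has an expected z of 1.960 + 0.842 = 2.802. At 0.01 the critical value is 2.576, so power is Φ(2.802 − 2.576) = Φ(0.226) = 0.589. Keeping 80% would need (2.576 + 0.842)²/(2.802)² = 1.49 times the patients.

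**The case against.** **The study is observational and its aim is tentative.** Family-wise control is not automatic for such a study, and this stands: a reader might infer that the plan must adjust for multiplicity, but nothing in the document obliges it to. Tentative wording is still not an exploratory designation. The SAP sets a significance criterion, and the correlation is sought in order to predict severity.

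**The large figures describe an analysis the plan does not state.** This also stands. From five markers and five times a reader might infer that the plan commits to 25 tests and a 72% false-positive chance, or 40 tests and 87%. The document says only that pain is assessed five times, not that five outcomes are modelled. The Background's reference to acute and chronic pain would equally allow two outcomes and 10 tests. Only the one-outcome case needs no assumption about extra outcomes.

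**The upper ends need independence.** Correct. The markers come from one blood sample, leukocytes and NLR share the neutrophil count, and the NRS is repeated in the same patients. The upper ends are ceilings, not expected values.

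**The multivariable step deals with the problem.** Only in part. It lowers the error (15-16% to about 12% for one outcome at correlations of 0.7) but does not bring it to 5%, because entry uses the same unadjusted 0.05.

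**Conclusion.** The concern holds in this form. The binary outcome and primary time point are undefined, and the stated rule exceeds 5% even in the most favourable case examined: one outcome with markers correlated at 0.9 still gives 8-9%. For one outcome the range is about 8-18%, and about 12% at correlations of 0.7. Only if all five times were analysed separately would it be about 22-62%, or about 40% at 0.7/0.7. All of these rest on the assumed sample sizes, higher-pain shares and correlations. The finding that the rule exceeds 5% held in every setting tried.

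Because therapy selection is among the aims, a reader might also infer that a false positive would alter patients' treatment. The document does not support that: it sets no marker cut-off and no treatment rule. The plan should be corrected, but the defect concerns how strong a claim the results can carry, not participant safety.

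**What to change.** Before analysis, define the binary pain outcome and one primary time point. For any predictor claim, replace the screen and backward selection with one logistic model per marker, adjusted for age, gender and BMI. Report the estimate and confidence interval for all five markers, whatever their P-values. Keep the backward model only as a labelled exploratory analysis. Then choose one route and state it:

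1. Label the whole analysis exploratory and claim no predictor from P<0.05.
2. Name one primary marker at the primary time point, keep 0.05 for it, and label the rest exploratory.
3. If a predictor claim is wanted for any of the five markers, apply Holm to the five adjusted P-values and label the other times exploratory.

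**Cost.** A few sentences in the SAP and no new data. Route 1 costs no power but gives up any claim of an established predictor. Route 2 keeps the power of the one primary test and leaves four markers exploratory. Route 3 reduces 80% power to about 59% at the first Holm step, or needs about 1.5 times the patients; thresholds relax after each rejection. Adjustment also needs enough higher-pain patients: at the smallest size assumed here, 60 × 0.30 = 18 such patients would support four coefficients (4.5 each), so a penalised fit may be needed.
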